7.2.8.1. Rescue medication use via the clip-on Propeller Sensor for MDI

A subset of participants from countries where the Propeller Sensor for MDI is available will also record rescue medication use via the clip-on Propeller Sensor for MDI. A supportive summary of rescue medication use via the clip-on Propeller Sensor for MDI for these participants will be presented.

Rescue medication use via the clip-on Propeller Sensor for MDI is defined in the same way as rescue medication use via the eDiary, except that the number of actuations will be used instead of the number of occasions in accordance with the way the data is captured.

7.2.8.2. Statistical analyses

The Mean Number of (on-treatment) Occasions of Rescue Medication Use Per Day will be summarised between each treatment group using means, standard deviations, medians, minimum and maximum.

The Percentage of (on-treatment) Rescue-Free Days will be summarised between each treatment group using means, standard deviations, medians, minimum and maximum.

Rescue medication use via the clip-on Propeller Sensor for MDI will be summarised in the same way as rescue medication use via the eDiary.

7.3. Exploratory Efficacy Analyses

7.3.1. Change from Day 84 in Clinic Visit trough FEV₁

Change from Day 84 in clinic visit trough FEV₁ measured post-bronchodilator is defined as:

FEV₁ measured prior to dosing and post-bronchodilator on Day X – Day 84 post-bronchodilator FEV₁

Where Day X is Day 112, Day 140 and Day 168.

Change from Day 84 in clinic visit trough FEV₁ measured pre-bronchodilator is defined as:

FEV₁ measured prior to dosing and pre-bronchodilator on Day X – Day 84 pre-bronchodilator FEV₁

Where Day X is Day 112, Day 140 and Day 168.

Participants who discontinue study treatment prior to Day 84 will be excluded from this analysis.

7.3.1.1. Statistical analysis

Change from Day 84 in Clinic Visit trough FEV₁ will be analysed using the same techniques as described for Change from baseline in CAT Total Score in Section [7.2.6.3](#).

A subgroup analysis of change from Day 84 in FEV₁ will be performed by including a treatment-by-severity-by-Day term in the Bayesian Repeated Measures model.

7.3.2. E-RS: COPD (Evaluating Respiratory Symptoms in COPD)

Change from baseline in E-RS: COPD and subscales will be summarised by treatment group. Exploratory analyses related to E-RS: COPD and subscales may be performed post SAC.

7.3.3. Measures of HCRU related to exacerbations

Unscheduled Healthcare Utilisation will be summarised separately for exacerbation-related, COPD-related or non-COPD related; each summary will be presented by all patients (i.e. moderate and severe index exacerbation combined), and separately by index exacerbation severity.

The number of days of hospital admission for the index and subsequent exacerbations will also be summarised by treatment group.

7.3.3.1. Re-hospitalisation within 30 days of index exacerbation

Re-hospitalisation within 30 days of index exacerbation is defined as 30 days from the date of hospital discharge until the date of next hospital admission (+ 1 day, to account for study day derivation), for participants who were hospitalised for their index exacerbation.

Exacerbation-related, COPD-related and Non-COPD-related hospital admissions are collected in separate eCRFs. The date of hospital admission is not collected in the COPD-related eCRF, therefore the date of next hospital admission will be estimated using the earliest of:

- Date of hospital admission for exacerbation-related hospitalisations
- Date of contact for COPD-related hospitalisations, where the number of inpatient hospitalisation days >0
- Date of hospital admission for non-COPD-related hospitalisations.

The proportion of participants who were re-hospitalised within 30 days of the index exacerbation will be summarised by each treatment arm.

7.3.3.2. Time from resolution of index exacerbation to next exacerbation

Time from resolution of index exacerbation to next exacerbation is defined as time from the date of (Investigator-defined) resolution of index exacerbation until the date of onset of the subsequent exacerbation.

A summary of time from resolution of index exacerbation to next exacerbation will be presented. Participants who did not have a subsequent exacerbation or for whom the index exacerbation was not resolved will be excluded from the summary.

Time from resolution of index exacerbation to next exacerbation will only be derived for the first subsequent exacerbation following the index exacerbation.

7.3.3.3. Subsequent exacerbation treatment type

A summary of the type of treatment for subsequent exacerbations (OCS, antibiotics, or both) may also be presented.

7.3.4. Compliance

Compliance with study treatment for all participants is captured from the dose counter on the ELLIPTA and the overall percentage compliance will be summarised by each treatment group.

Reported compliance with study treatment is also captured daily in the eDiary from the question "Did you take this morning's dose of study medication"?

The percentage of reported compliance for each participant is calculated as:

(Sum of the number of days where the question was answered with ‘Y’) / (Number of days from first dose of study treatment to last dose of study treatment) x 100

Overall percentage of reported compliance will also be summarised by each treatment group.

7.3.4.1. Number of actuations of double-blind study treatment measured by the clip-on Propeller Sensor

Percentage compliance via the clip-on Propeller Sensor for ELLIPTA in the subset of participants from countries where the Propeller Sensor for ELLIPTA is available is calculated as:

(Sum of the number of days with actuation > 0) / (Number of days from first dose of study treatment to last dose of study treatment) x 100

Overall percentage compliance will be summarised by each treatment group.

7.3.4.2. Missing EXACT-PRO data

Missing EXACT-PRO data will be summarised by treatment group.

7.3.5. Inflammatory/infective markers in blood and sputum in relation to acute exacerbation of COPD

Results of the analysis of blood/spontaneous sputum samples of eosinophil counts and inflammatory/infective mediators/markers will be summarised by treatment group.

Further analyses of inflammatory/infective markers may be performed, for example split by CRP high, CRP low, Procalcitonin high, etc. categories.

7.3.6. Other spirometry measurements

Percent predicted FEV₁, Forced Vital Capacity (FVC), percent predicted FVC and FEV/FVC ratio will be summarised by treatment group.

7.3.7. Other symptoms suggestive of exacerbation

Responses to questions in the eDiary related to symptoms of sputum purulence (colour), fever, sore throat, wheezing and colds collected in the eDiary will be listed by treatment group.

7.3.8. Classification of exacerbating COPD participants and prediction of response to nemiralisib using machine learning techniques

Exploratory analysis of endpoints using machine learning techniques will be performed which will include classification of COPD participants, identification of parameters which describe a responder, and prediction of response to nemiralisib using baseline data. Details of these analyses will be described in a separate RAP and results may be reported separately to the CSR.

8. SAFETY ANALYSES

The safety analyses will be based on the Safety population, unless otherwise specified. The details of the planned displays will be provided in [Appendix 11: List of Data Displays](#).

8.1. Adverse Events Analyses

Adverse events analyses including the analysis of adverse events (AEs) and Serious (SAEs) will be based on GSK Core Data Standards.

8.1.1. Adverse Events of Special Interest

Adverse events of special interest (AESI) are significant identified or potential risks identified in the nemoralisib clinical development programme.

8.1.1.1. Post-inhalation Cough Immediately Following Dosing

Post-inhalation cough immediately following dosing is an AESI and will be evaluated during study Visits 2-6 in the 12-Week Double-Blind Treatment Period. Investigators (or medically qualified designees) will monitor participants for potential study treatment tolerability issues, including post-inhalation cough, within 5 minutes immediately following dosing.

The percentage of patients experiencing post-inhalation cough following dosing, regardless of whether it was also reported as an AE, overall and by each visit will be summarised for each treatment group. The type of cough, time to onset and duration of cough, and severity will also be summarised.

In addition, any post-inhalation cough immediately following dosing reported as an adverse event during the clinic visit observation or during the course of the study will be summarised by treatment group.

8.1.1.2. Paradoxical bronchospasm

Paradoxical bronchospasm is an AESI, defined using the Preferred Terms Bronchospasm and Bronchospasm paradoxical and will be summarised by treatment group.

8.2. Clinical Laboratory Analyses

Laboratory evaluations including the analyses of Chemistry laboratory tests, Haematology laboratory tests and liver function tests will be based on GSK Core Data Standards.

8.3. Other Safety Analyses

The analyses of non-laboratory safety test results including ECGs and vital signs will be based on GSK Core Data Standards, unless otherwise specified.

8.4. Mortality

A summary of all-cause mortality by treatment will be presented.

9. PHARMACOKINETIC ANALYSES

9.1. Population of Interest

The primary pharmacokinetic analyses will be based on the “Pharmacokinetic” population, unless otherwise specified.

9.2. Drug Concentration Measures

Plasma nemiralisib concentrations of GSK2269557 will be listed and summarised by dose, day and time. Drug levels will be summarised by day (14, 28), dose and time intervals (trough, 0-<1h, 1-6h).

Refer to [Appendix 4: Data Display Standards & Handling Conventions \(Section 13.4.3 Reporting Standards for Pharmacokinetic\)](#).

Details of the planned displays are provided in [Appendix 11: List of Data Displays](#) and will be based on GSK Data Standards and statistical principles.

10. POPULATION PK ANALYSIS

A dataset for population PK analysis will be provided by Statistics and Programming based on the NONMEM data specifications in Section 13.8.2.

Conduct of the population PK analyses will be based on the current guidance which contains specific recommendations for working practices, processes and standards for population PK and PK/PD analysis conducted by Clinical Pharmacology Modelling and Simulation (CPMS) [Analysis & Reporting, 2017].

The sparse PK samples will be subjected to a validated population PK model for nemiralisib currently under development.

Details of these analyses will be described in a separate CPMS RAP and results will be reported separately to the CSR. Analyses and reporting of the population PK model will be in accordance with the FDA and EMEA guidance on population PK, PK-PD analyses.

10.1. Derived Pharmacokinetic Parameters

The exposure parameters (e.g. AUC, C_{max}) will be derived from the individual post-hoc estimates from the POP PK model. These will be summarized across dose treatments, subgroups (e.g., gender, race) or as a function of a continuous variable (e.g., age).

11. PHARMACOKINETIC / PHARMACODYNAMIC ANALYSES

If statistical analyses suggest an effect of nemiralisib on primary and other key clinical endpoints, an integrated longitudinal population dose/exposure versus clinical response on analysis key parameters including FEV₁ and exacerbation rate will be undertaken. Participant characteristics influencing the relationship will be evaluated.

Details of these analyses will be described in a separate CPMS RAP and results will be reported separately to the CSR.

13. APPENDICES

13.1. Appendix 1: Protocol Deviation Management and Definitions for Per Protocol Population

13.1.1. Exclusions from Per Protocol Population

Protocol deviations will be reviewed regularly throughout the course of the study, as described in Protocol Deviation Management Plan (PDMP). Deviations which will result in exclusion from the Per Protocol population will be assigned on a case-by-case basis prior to database freeze (DBF).

Decisions on whether or not the subject should be excluded from the PP population because the incorrect treatment was taken, due to the incorrect container being dispensed, will be identified after unblinding (i.e. post DBF). A PD of “incorrect treatment” will be added to the reporting dataset.

13.2. Appendix 2: Assessment Windows

13.2.1. Definitions of Assessment Windows for Analyses

13.2.1.1. Hospital discharge

As per Section 5.1 of the Protocol, if discharge takes place between Day 11 and Day 17 (inclusive), the assessments planned for Day 14 may be completed on the day of discharge. In these cases, for this endpoint only, the FEV₁ assessment will be assigned the hospital discharge FEV₁ assessment and the Day 14 assessment will be missing.

For all other analyses and summaries that include participants who were hospitalised for their index exacerbation, an additional Analysis Timepoint of “HOSPITAL DISCHARGE” will be derived. However, in the cases where discharge takes place between Day 11 and Day 17 (inclusive), participants will be summarised under DAY 14 and a footnote to say that participants who were discharged at Day 14 are summarised under DAY 14 will be included.

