2.1. Study Objective(s) and Endpoint(s)

Objectives	Endpoints
Primary Objectives	Primary Endpoints

 To characterise the dose response of nemiralisib administered in addition to SoC compared with placebo and SoC in participants diagnosed with an acute moderate or severe exacerbation of COPD 	
 Change from baseline in Clinic Visit trough forced expiratory volume in one second (FEV₁) at Day 84 measured post-bronchodilator
Secondary Objectives	Secondary Endpoints

 To characterise the dose response and efficacy of nemiralisib administered in addition to SoC compared with placebo and SoC in participants diagnosed with an acute moderate or severe exacerbation of COPD 	
 Rate of moderate and severe exacerbations over the 12-Week Treatment Period Time to next moderate/severe exacerbation following index exacerbation Change from baseline in Clinic Visit trough FEV₁ measured pre- and post-bronchodilator at Days 14, 28, 56, and 84 (Day 84: post-bronchodilator is the primary endpoint; pre-bronchodilator is a secondary endpoint) and at hospital discharge (only for participants who are hospitalized for the index exacerbation) Change from hospital discharge in clinic visit trough FEV₁ measured pre- and post-bronchodilator at Days, 14, 28, 56, and 84 (in participants hospitalized for index exacerbation only)

 To evaluate the treatment effect of nemiralisib in addition to SoC compared with placebo and SoC on symptoms indicative of an exacerbation and on health status using Patient-Reported Outcomes (PROs) in participants diagnosed with an acute moderate or severe exacerbation of COPD 	
EXAcerbations of Chronic Pulmonary Disease Tool (EXACT-PRO)
 
 Proportion of participants achieving the EXACT definition of recovery from the index exacerbation by Days 14, 28, 56, and 84 Time to recovery from index exacerbation Severity of subsequent HCRU-defined exacerbation(s) defined by EXACT 
COPD Assessment Test (CAT)
 
 Proportion of responders using the CAT at Treatment Days 28, 56, and 84, and following EXACT defined

Objectives	Endpoints

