7.2.4. Change from hospital discharge in clinic visit trough FEV₁

Change from hospital discharge in clinic visit trough FEV₁ will be derived only for participants who were hospitalised for their index exacerbation and who have been subsequently discharged.

Change from hospital discharge in clinic visit trough FEV₁ measured post-bronchodilator is defined as:

FEV₁ measured prior to dosing and post-bronchodilator on Day X – FEV₁ measured post-bronchodilator and prior to dosing on day of hospital discharge.

Where Day X is 14, 28, 56 and 84.

Change from hospital discharge in clinic visit trough FEV₁ measured pre-bronchodilator is defined as:

FEV₁ measured prior to dosing and pre-bronchodilator on Day X – FEV₁ measured prior to dosing and post-bronchodilator on day of hospital discharge.

Where Day X is 14, 28, 56 and 84.

Note, as per Section 5.1 of the Protocol, if discharge takes place between Day 11 and Day 17 (inclusive), the assessments planned for Day 14 may be completed on the day of discharge. In these cases, for this endpoint only, the FEV₁ assessment will be assigned the hospital discharge assessment and the Day 14 assessment will be missing. Refer to Section 13.2.1.1 for further details.

In addition, if discharge takes place after Day 14, the Day 14 assessment will be missing for this analysis.

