13.2.1.2. EXACT-Defined Recovery for CAT Trigger

If the study day following EXACT-defined recovery for a participant occurs within a scheduled assessment window, an additional analysis time-point will be programmatically created for that scheduled visit. For example, if EXACT-defined recovery occurred on Day 56, then a Day 56 Visit will be programmatically created with the data from the Recovery visit so that it can be summarised/analysed in both the Visit and Recovery categories.

Due to software limitations of the electronic PRO device, the study day following EXACT-defined recovery from the index exacerbation is not derived according to the EXACT User Manual. Instead, it has been derived using a 3-day Rolling Average that is calculated as the mean EXACT score [Day X-2, Day X-1, Day X].

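### The HOSPITAL DISCHARGE row for change from baseline in trough FEV1 omits participants discharged on Days 11 to 17

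*SAP*

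**What the plan says.** SAP section 2.1 has two secondary endpoints that involve FEV1 and hospital discharge.

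- **Change from baseline, at discharge.** Trough FEV1 is compared with baseline at the scheduled days "and at hospital discharge (only for participants who are hospitalized for the index exacerbation").
- **Change from discharge.** Trough FEV1 at Days 14, 28, 56 and 84 is compared with the value on the day of discharge.

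Day 14 assessments may be done at discharge if discharge falls on Days 11 to 17. For change from discharge, section 7.2.4 resolves the overlap in favour of discharge: the FEV1 "assessment will be assigned the hospital discharge assessment and the Day 14 assessment will be missing".

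For everything else, section 13.2.1.1 resolves it the other way. It begins "For all other analyses and summaries that include participants who were hospitalised for their index exacerbation" and sets up a HOSPITAL DISCHARGE timepoint. It then adds that, for discharges from Day 11 to Day 17, "participants will be summarised under DAY 14 and a footnote" will be included, stating that "participants who were discharged at Day 14 are summarised under DAY 14".

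The next subsection, 13.2.1.2, meets a similar overlap for CAT, when the assessment after EXACT recovery falls within a scheduled window. There the record is copied "so that it can be summarised/analysed in both the Visit and Recovery categories".

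**The concern.** Section 7.2.3 defines change from baseline only at the scheduled days, so 13.2.1.1 is the only rule that builds the discharge timepoint for the first endpoint. Under that rule, whether a participant appears in the row depends on the day of discharge. That day is observed after randomisation and treatment may affect it. The row then describes a selected subset of discharged participants, and the share left out may differ by arm.

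The footnote restores no data. It also names Day 14 where the rule covers Days 11 to 17, so a reader would underestimate who is absent.

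The same row is planned at Interim Analyses 1 and 2 (13.11.6.1 and 13.11.6.2). Section 3.1 lets the sponsor set the severity stratification proportions after Interim Analysis 1 by inspecting all available endpoints.

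**Working it through.** **Step 1. Follow each discharge day through the rules.**

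| Day of discharge | Change from baseline at discharge (13.2.1.1) | Change from discharge (7.2.4) |
|---|---|---|
| Up to Day 10 | In the HOSPITAL DISCHARGE row | Discharge value used |
| Days 11 to 17 | Under DAY 14 only | Discharge value used; Day 14 set to missing if the assessment was combined |
| Day 18 or later | In the HOSPITAL DISCHARGE row | Discharge value used; Day 14 missing |

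Late discharge is foreseen: section 7.2.4 says that "if discharge takes place after Day 14, the Day 14 assessment will be missing for this analysis". The redirect to DAY 14 stops at Day 17, so what is omitted is a middle band.

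**Step 2. Find where the row is used.** The list of displays asks for an extra discharge row for the Severe group in Tables 2.2 and 2.4. Their shell (Example 3) shows n, mean, SD, median, minimum and maximum by arm, with no treatment difference or posterior probability. The dose-response outputs are at Days 14, 28, 56 and 84, and the repeated measures model in 7.1.3 uses scheduled visits. No model is planned at discharge.

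**Step 3. Write the distortion.** Let f be the share of discharged participants who leave on Days 11 to 17, R the mean change among those retained and O the mean among those omitted.

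- Mean of all discharged = (1 − f) × R + f × O
- Row mean − mean of all discharged = R − [(1 − f) × R + f × O] = f × (R − O)

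The plan has no figure for f or R − O, so there is nothing to reproduce. The following are assumptions:

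- f = 5%, difference 50 mL: 0.05 × 50 = 2.5 mL
- f = 20%, difference 100 mL: 0.20 × 100 = 20 mL
- f = 25%, difference 150 mL: 0.25 × 150 = 37.5 mL

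These are absolute sizes. The sign is that of R − O, which is unknown because the retained group mixes shorter and longer stays.

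If f were 25% in one arm and 10% in another, with the same 100 mL difference in both, the gap between the two row means would shift by (0.25 − 0.10) × 100 = 15 mL. This is again an assumption.

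**Step 4. After the change.** If Day 11 to 17 discharges also appear in the discharge row, nobody is omitted on account of discharge day, f = 0 and the term f × (R − O) vanishes.

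**Step 5. A related gap.** Doing the Day 14 assessments at discharge is optional, yet the redirect depends on discharge date alone. A participant discharged on Day 11 who also attends a Day 14 visit has two candidate values for DAY 14, and section 13.5.1 has no rule for choosing between them.

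**The case against.** The strongest reply is that nothing is lost. The values are reported under DAY 14, by a prespecified rule with a footnote, in tables that only describe the data. This stands, and it limits the consequences to how a descriptive row is read.

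Two wider inferences are tempting and should be resisted.

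- A reader might think that the modelled discharge endpoint is damaged. It is not: change from discharge, which 7.2.4.1 plans to analyse by repeated measures if numbers allow, keeps these participants.
- A reader might think that a planned between-arm comparison at discharge is biased. No such comparison is specified. The risk lies in informal reading of arm means side by side.

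It is also fair to say that completing the row does not make discharge a fair time point for comparing arms. Participants are measured on different days, set by their own length of stay, so a dose that shortened stay would still be measured earlier than placebo.

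Finally, the CAT rule is not an exact parallel. It copies an event-triggered record into the scheduled visit, whereas here the scheduled row is already filled and the event row is left short. The principle of showing one assessment under both labels carries over, and none of these points explains why the discharge row should be incomplete.

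**Conclusion.** The point holds in a limited form. For change from baseline in trough FEV1 at hospital discharge, the HOSPITAL DISCHARGE row in Tables 2.2 and 2.4 omits participants discharged on Days 11 to 17, a group chosen by a post-randomisation outcome. The primary Day 84 analysis is untouched.

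A reader might infer that the rule removes the longest stays and leaves only early dischargers, so that the row mean is too high. The plan does not support this: discharges from Day 18 stay in the row, and without data on R − O no direction can be stated. The range of 2.5 to 37.5 mL rests wholly on assumed shares and differences and only shows how the error scales.

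This is a defect of completeness and labelling in a listed secondary endpoint. It is worth correcting because the correction costs almost nothing.

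**What to change.** In section 13.2.1.1, for all analyses and summaries outside 7.2.4:

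1. Give every participant discharged on Days 11 to 17 a HOSPITAL DISCHARGE record from the discharge-day FEV1.
2. If that assessment also served as the Day 14 visit, create a DAY 14 record from the same value. If a separate Day 14 visit took place, use that visit for DAY 14.
3. Reword the footnote to say that it concerns discharges on Days 11 to 17 and that participants whose discharge assessment served as Day 14 appear in both rows.

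The cost is a sentence or two of text and one derivation step of the kind already specified for CAT in 13.2.1.2. No new data are needed and no model changes. The text should not present the completed row as a treatment comparison.
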